A Megastudy of Single-Session Interventions for Depression (Includes analysis plan and
consent form) March 8, 2025

Protocol

Design

Participants will be randomly assigned to one of 13 conditions, with even odds of allocation, except that the passive control condition will have 3X odds of allocation. Researchers will use Qualtrics's "evenly present elements" feature to ensure each condition gets a roughly equal number of participants.

Procedure

1. **Screen.** Participants will be asked to complete the Patient Health Questionnaire (9-item, PHQ-9) to assess eligibility. Next, eligible participants will be asked to consent to participate in the study.
2. **Baseline session.** Participants who consented will immediately begin the first study session, starting with a baseline well-being questionnaire. Next, they will be randomly allocated to one of the 11 experimental SSI conditions, an active comparison SSI condition, or a passive control condition. After they complete the condition to which they were randomized, they will respond to some of the baseline measures again, as well as measures of SSI satisfaction.
3. **Follow-up.** Four weeks later, participants will be invited to a follow-up survey, in which they will complete the baseline well-being survey again.

Participants will be compensated directly after completing each study session. If participants drop out of the baseline session after randomization, they will still be invited to complete the follow-up survey. After each study session, participants will be offered access to a list of online mental health resources (see <https://osf.io/wz5u6>).

Measures

See the "Megastudy Measures" document (<https://osf.io/76cfy>) for information on measures, and the "Timepoints of megastudy measures" document (<https://osf.io/hn83p>) for information on measurement timepoints.

To measure depressive symptoms, researchers will use the reliable and valid Patient Health Questionnaire (9-item). Researchers will consider a change in PHQ-9 score of 5 or greater to be clinically meaningful (Kroenke, 2012). To measure agency, researchers will use the Pathways Subscale of the State Hope Scale, a reliable and valid three-item self-report measure of one's perceived ability to generate plans and work toward goals. To measure hopelessness, researchers will use the reliable 4-item Beck Hopelessness Scale. Researchers will measure depression change expectancies using three items from the

Depression Expectancies for Change scale (those with the highest item-total correlations in the original paper on the scale). Researchers will measure participants' positive actions and thoughts (aligning with the goals of cognitive-behavioral therapy) using the Frequency of Actions and Thoughts Scale (FATS). Researchers will also include two multiple-choice questions regarding participants' readiness to make changes toward challenging their depression.

Researchers will measure how acceptable participants find the SSIs with the Credibility / Expectancy Questionnaire, a few items asking if one experienced an Aha! moment during the SSI and how strongly the Aha! moment affected them, and a rating (out of 5 stars) of the intervention's overall quality.

References:

Kroenke K. (2012). Enhancing the clinical utility of depression screening. *CMAJ : Canadian Medical Association journal*, 184(3), 281–282. <https://doi.org/10.1503/cmaj.112004>

Interventions

11 *experimental SSIs* were included for testing. The active comparison SSI is the Action Brings Change Project, an evidence-based SSI for depression. The *passive control* condition aims to hold attention without influencing depressive symptoms or mood (a three-minute video, multiple-choice questions, two-minute reading passage, three-minute writing exercise, all about trout). All 11 experimental SSIs, the active comparison SSI, and the passive control condition are available in browser (<https://osf.io/nqdte>) and downloadable versions (<https://osf.io/ujbdf>).

Data Collection

Researchers have not yet started data collection. Participants will be recruited from the online participant recruitment platform CloudResearch Connect and, if needed, CloudResearch and Prolific. All study activities will take place through the online survey and experience management platform Qualtrics, except participants will be invited to participate in each study session and be compensated through their online recruitment platform. Participants can choose to skip any items in the study, except ones that are critical for an intervention to function properly.

Hypotheses

Primary Hypothesis

For each SSI, we hypothesize that participants assigned to the SSI will report a different extent of change in depressive symptoms between baseline and four-week follow-up than participants assigned to the passive control condition.

Secondary Hypotheses

1. For each experimental SSI, researchers hypothesize that participants assigned to the SSI will report a different extent of change in depressive symptoms from baseline to four-week follow-up than participants in the active comparison condition.
2. For each SSI, researchers hypothesize that participants assigned to the SSI will report a different extent of change in each secondary well-being outcome (agency, hopelessness, depression change expectancies, readiness for change, frequency of positive actions and thoughts) compared to participants in the passive control. researchers will compare change in all outcomes from baseline to four-week follow-up, as well as from baseline to immediate post-intervention for outcomes collected at all three timepoints.
3. For each experimental SSI, researchers hypothesize that participants assigned to the SSI will report a different extent of change in each secondary well-being outcome (from baseline to week four or baseline to post-intervention) than those assigned to the active comparison condition.
4. For each experimental SSI, researchers hypothesize that participants will rate the SSI as differently acceptable than the active comparison SSI according to CEQ scores, star ratings, and rate of Aha! Moments.
5. We hypothesize that participants who expect they can improve their depression more at baseline will show a different change in depressive symptoms from baseline to week four.
6. We hypothesize that, on average, the SSIs will be more effective at improving all well-being outcomes (from baseline to week four or baseline to post-intervention) than the passive control.

We do not make any specific hypotheses about which SSIs will be more effective or acceptable than others.

Statistical Analysis Plan

Inclusion criteria

Participants will need to be at least 18 years old, be able to read and write fluently in English, and have enough access to the internet to complete two sessions over four weeks. They must also score at least 10 on the PHQ-9 screen (suggesting moderate depression) and pass the bot check (<https://osf.io/kba7v>) during the screen (Kroenke et al., 2001).

All participants who are randomized to an experimental condition (and therefore completed all baseline measures) will be included in analyses. If a participant begins a survey multiple times, researchers will only keep data from the first time.

Please see the measures document (<https://osf.io/76cfy>) and the data cleaning script (<https://osf.io/jpk38>) for details on measures and recoding. Before sharing the study data, researchers will remove any potentially identifiable information, included in written response items. Deviations from this pre-registration will be documented.

References:

Primary analysis

Researchers will use a mixed-effects linear regression model to test if depressive symptoms decrease more from baseline to four-week follow-up in each of the 12 active conditions compared to the passive control condition. Timepoint is a three-level factor (i.e., baseline, post-test, and week 4 follow up). The model will include a participant identifier as a random intercept.

Using the “lme4” and “lmerTest” packages in R, this analysis will take this form:

```
lmer(depressive_symptoms ~ timepoint * condition + (1|participant_id))
```

Using lmerTest’s default, p-values will be calculated using Satterthwaite’s method for denominator degrees of freedom.

Secondary analyses (matching the hypotheses above):

1. To test if each experimental SSI changes PHQ-9 scores differently from the active comparison SSI, researchers will redo the main analysis, except using the active comparison condition as the comparator.

2. To test if each SSI changes secondary well-being outcomes to a different extent than the passive control, researchers will replicate the primary analysis for each secondary outcome. For outcomes measured at three timepoints, researchers will compare baseline to each timepoint.
3. To test if each experimental SSI changes secondary well-being outcomes to a different extent than the active comparison SSI, researchers will redo analysis #2, but instead use the active comparison SSI as the comparison condition.
4. To test if each experimental SSI differs in acceptability from the active comparison SSI, researchers will conduct a linear regression model testing between-group differences in intervention acceptability for each acceptability outcome at each timepoint the outcome was collected. For these analyses, researchers will drop data from the passive control because it does not make sense to compare satisfaction with a mental health intervention to satisfaction with an educational program about trout.
5. To test if participants who expect that they can change their depression more at baseline will show a different reduction in depressive symptoms from baseline to week four, researchers will run a linear mixed-effects regression model with depressive symptoms as the DV, timepoint, baseline depression expectancies, and the interaction between the two as predictors, and a participant identifier nested in experimental condition as a random intercept.
6. To test if, on average, the SSIs will change each outcome differently than the passive control, researchers will re-run the main analysis with *experimental condition* re-coded into a two-level factor in which any of the 12 active SSIs will be coded as “active.” The random intercept, participant ID will be nested within experimental condition. For outcomes measured at three timepoints, researchers will compare the baseline to each timepoint

Sensitivity analyses:

1. Researchers will re-run the primary analysis with demographic covariates: age, gender, disability, race, education, relationship status, political party, employment status, household income, and perceived socioeconomic standing (Social Ladder).
2. Researchers will re-run the primary analysis with demographic and baseline mental health covariates: age, gender, disability, race, education, relationship status, political party, employment status, household income, perceived socioeconomic standing (Social Ladder), baseline depression change expectancies, baseline

positive actions and thoughts, baseline readiness for change, baseline agency, and baseline hopelessness.

3. Researchers will test for differential attrition across conditions and by the interaction of condition and each covariate. If researchers find evidence for differential attrition, researchers will conduct a sensitivity analysis re-running primary and secondary analyses accounting for differential attrition using inverse probability weighting. See the analysis script (<https://osf.io/5eya3>) for details.

Robustness Check: Researchers will not correct for multiple hypotheses in primary and secondary analyses because each test of an intervention's effect is viewed as a separate hypothesis. However, it might be that some statistically significant results detected are false positives that occur due to testing so many hypotheses at once. To examine this possibility, researchers will conduct a robustness check that replicates all analyses that compare an outcome across many conditions correcting for multiple hypotheses using the Benjamini-Hochberg procedure (Benjamini & Hochberg, 1995).

Inference Criteria: P-values will be used as the criterion for statistical significance. Two-sided tests will be used for all analyses. Effects of $p \leq .05$ will be reported as significant, $.05 < p \leq .1$ as marginally significant, and $p > .1$ as nonsignificant.

Missing data handling: Because participants can choose to skip items, there may be some missing data within outcome measures. If one's response to a scale is missing 33% of its items or fewer, researchers will impute a value for each missing item using the mean of the other items of the scale that the participant answered.

If an outcome scale is missing more than 33% of its items, researchers will consider the entire scale to be missing. In these cases, researchers will not impute missing outcome data because linear mixed models' estimates for longitudinal clinical trial data are not improved by outcome data imputation (Chakraborty & Gu, 2009). Researchers will impute missing covariate data as described in the cleaning script (<https://osf.io/jpk38>).

Sample Size: Researchers will aim to recruit 500 participants per intervention condition, except that the passive control condition will have 3X as many participants as the other conditions because it will improve the statistical power of analyses comparing conditions to the passive control. Thus, researchers aim for a total baseline sample size of $n = 7,500$. This sample size will enable us to detect change in depressive symptoms from baseline to follow-up between each intervention condition and the passive condition with an effect size smaller than Cohen's $d = 0.17$, with 90% power and alpha = 0.05. This sample size will also allow us to detect differences in change in depressive symptoms from baseline to follow-up between each intervention condition smaller than $d = 0.19$.

References:

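### The keep-first-start rule has no completeness condition, so at week 4 it can discard a complete PHQ-9 in favour of an abandoned attempt

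*Combined protocol and SAP*

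**What the plan says.** Two adjacent sentences under Statistical Analysis Plan, Inclusion criteria, govern who and what is analysed. The first sets the population: "All participants who are randomized to an experimental condition (and therefore completed all baseline measures) will be included in analyses". The second deals with repeat starts: "If a participant begins a survey multiple times, researchers will only keep data from the first time". Neither states an exception or says which is applied first.

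The Protocol, Procedure, describes two occasions that the second sentence can reach. In the baseline session, questionnaires come before allocation: "Participants who consented will immediately begin the first study session, starting with a baseline well-being questionnaire". Week 4 is a separate survey: "Four weeks later, participants will be invited to a follow-up survey, in which they will complete the baseline well-being survey again".

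Missing data handling then fixes what happens to a partly answered scale: "If an outcome scale is missing more than 33% of its items, researchers will consider the entire scale to be missing". It continues: "In these cases, researchers will not impute missing outcome data".

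The SAP refers to a measures document and a data cleaning script "for details on measures and recoding". Neither file was available for this review.

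**The concern.** The trigger for the duplicate rule is beginning a survey. It does not ask whether the first attempt was finished, whether it contained the PHQ-9, or whether it reached randomisation.

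For the randomised session there is a good reason to let the first exposure count: someone allocated twice should be analysed under the first allocation. That reason does not carry over to week 4, where nothing is delivered and there is no first exposure to protect. A participant who opens the follow-up, is interrupted before the PHQ-9 and later completes it in a new record has supplied a valid primary outcome. The literal rule replaces it with a blank one.

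Two things are at stake. Observed primary outcomes become missing data that will not be imputed. Those participants would also look like dropouts in the differential-attrition test planned under Sensitivity analyses, although they responded. Because week-4 interruption happens after exposure, it could differ by arm, but nothing in the documents shows that it would.

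A second, more conditional problem arises at baseline. A first start can end before allocation and a second can be randomised. Depending on the order of data cleaning, the record that holds the allocation could be removed.

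**Working it through.** **Step 1: when the week-4 loss occurs.** All of the following must hold:

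1. The participant starts the follow-up more than once, and the return creates a new record instead of resuming the old one.
2. The first attempt stopped with more than 33% of the PHQ-9 items unanswered. With 9 items, three missing is 3/9 = 33.3%. Taken literally, fewer than seven answers make the scale missing; if 33% stands for one third, fewer than six do.
3. A later attempt contains a scorable PHQ-9.

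The duplicate rule then keeps the first record, the 33% rule sets its PHQ-9 to missing, and the no-imputation rule leaves it missing. An abort after the PHQ-9 has been answered costs no primary outcome.

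**Step 2: when the baseline loss occurs.** There are two possible orders of cleaning.

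- Define the randomised set, then remove duplicates: the unrandomised first start was never in the set, so the person stays in.
- Remove duplicates, then define the randomised set: the second start, which holds the allocation, is gone, so the person drops out despite having been randomised.

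The documents do not give the order.

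**Step 3: reproduce the plan's own figures (Sample Size).** Inputs: 500 in each of 12 active arms, three times as many in passive control, 90% power, two-sided alpha 0.05, standardised SD of 1, no dropout.

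- Total: 12 × 500 + 1,500 = 7,500, as stated.
- Detectable d = (1.960 + 1.282) × √(1/500 + 1/1,500) = 0.167, consistent with the stated bound of 0.17.
- Power at d = 0.17 is 90.9%.

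**Step 4: size of the week-4 loss.** The documents give neither a restart rate nor a retention rate, so these are assumptions: a share r of week-4 responders with an aborted first start of 1%, 3% or 5%, and 6,000 (80% retention) to 7,500 (100%) responders. Outcomes lost are at most r × responders. The standard error grows by at most 1/√(1 − r) − 1. Power is at d = 0.17 with no other attrition.

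| r | Lost of 6,000 | Lost of 7,500 | SE increase | Power |
|---|---|---|---|---|
| 0 | 0 | 0 | 0 | 90.9% |
| 1% | 60 | 75 | 0.5% | 90.6% |
| 3% | 180 | 225 | 1.5% | 90.0% |
| 5% | 300 | 375 | 2.6% | 89.4% |

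These are upper bounds for each r. They count every abort as a lost PHQ-9, which Step 1 shows is not so, and they give no credit for the affected participants' earlier measurements, which stay in the mixed model.

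With an assumed 20% ordinary attrition, power at d = 0.17 is 83.8% with no restart loss, 83.4% at r = 1% and 81.9% at r = 5%.

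**The case against.** The strongest reply is that this is a matter of wording. The first sentence of the pair defines who is analysed and the second only chooses between records, so read in that order nobody randomised is lost. The platform may resume an interrupted session or block restarts, and the PHQ-9 may come early in the follow-up. The numerical effect is small, affected participants still contribute earlier data, and differential attrition is to be tested, with inverse probability weighting if it is found. A strict first-start rule may also serve a purpose: sessions are paid, and it stops someone who failed the PHQ-9 screen or bot check from trying again, if the screen and baseline share one survey.

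Much of this stands. A reader might infer that the two Inclusion criteria sentences flatly contradict each other. The documents do not support that, because the conflict depends on an unstated order of cleaning. A reader might also infer that the rule undoes the commitment that "If participants drop out of the baseline session after randomization, they will still be invited to complete the follow-up survey". It does not: the rule works survey by survey, and such a person's first follow-up start is treated like anyone else's. The point about re-entry after a failed screen is fair, and the fix has to allow for it.

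What does not fall away is the week-4 case. There the text states a rule and, followed as written, the rule keeps the worse record. The unseen cleaning script might narrow it, but the SAP cites that script for recoding and covariate imputation, not for duplicates.

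**Conclusion.** The point holds for the follow-up survey as worded, and conditionally for the baseline session. At week 4 the rule can discard a complete primary outcome for no benefit, provided that a return opens a new record and the first attempt stopped short of a scorable PHQ-9. At baseline it could drop a randomised participant only if duplicates are removed first.

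The size is small. On the assumed rates, the cost is at most 60 to 375 outcomes and a 0.5% to 2.6% larger standard error. The power calculation has little slack, since about 3% uniform loss uses up the margin above 90%, but even 5% costs only about 1.5 percentage points (90.9% − 89.4%) before other attrition.

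It would be tempting to read the lost-outcome counts as an expected loss, or to claim a bias. Neither is supported: the rates are assumed, the counts are ceilings, and no direction of bias can be shown. An abort before randomisation cannot depend on the arm; one at week 4 could, but the documents are silent. This is a minor, avoidable defect.

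**What to change.** Replace the single sentence with a rule for each survey:

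- **Follow-up:** keep the first attempt with a scorable PHQ-9 under the 33% rule.
- **Baseline session:** define the analysis set first. Keep the first attempt that reached randomisation and analyse it under the first-assigned condition. Continue to exclude anyone who had earlier failed the PHQ-9 screen or the bot check.

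It would also help to state whether resuming a saved session counts as a new start, and to report the number of duplicate starts by arm so that readers can judge how much the rule mattered.

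The cost is a few sentences in the SAP and a small edit to the cleaning script, which must check for earlier failed screens. A retained follow-up may be dated slightly later than the first click. The Data Collection section says recruitment has not begun, so the change can be made before any data exist and need not be recorded later as a deviation.

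### A participant intercept alone gives every change score the same variance, so post-test and week-4 standard errors for three-timepoint outcomes can be wrong; an unstructured covariance avoids this at almost no cost

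*Combined protocol and SAP*

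**What the plan says.** The Primary analysis section of the SAP sets out a linear mixed model for depressive symptoms with timepoint, condition and their interaction. It states: "The model will include a participant identifier as a random intercept". The formula beside it, "lmer(depressive_symptoms ~ timepoint * condition + (1|participant_id" (closing brackets cut), has no other random term. On time it states: "Timepoint is a three-level factor (i.e., baseline, post-test, and week 4 follow up" (closing bracket cut). P-values use Satterthwaite degrees of freedom.

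The model is then reused:

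- Secondary analyses, item 2 (SSIs against passive control): "researchers will replicate the primary analysis for each secondary outcome. For outcomes measured at three timepoints, researchers will compare baseline to each timepoint".
- Item 3 (experimental SSIs against the active comparison): "researchers will redo analysis #2, but instead use the active comparison SSI as the comparison condition".
- Item 6 (all active SSIs pooled against passive control): "The random intercept, participant ID will be nested within experimental condition".

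Secondary Hypotheses, item 2, asks for change to week four, "as well as from baseline to immediate post-intervention for outcomes collected at all three timepoints". Procedure, item 2, places the post-test in the baseline session: "After they complete the condition to which they were randomized, they will respond to some of the baseline measures again". The follow-up survey comes four weeks later.

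The text names no unstructured covariance, random slope or robust standard error. It gives no correlations, SDs or expected dropout. The list of measures taken at each timepoint is in a linked document that was not available for this review.

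**The concern.** With only a participant intercept, the model assumes one residual variance and one correlation for every pair of readings. Baseline and post-test are taken in one sitting; week 4 is a month away. Nothing in that schedule suggests that the three change scores vary equally. If they do not, the single variance is too small for some contrasts and too large for others.

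The SAP decides significance by p-value and leaves the main tests uncorrected for multiplicity, so the calibration of each test matters. Each three-timepoint outcome has 12 SSI-versus-passive contrasts at week 4 and 12 at post-test.

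Nothing described elsewhere relaxes the structure. Satterthwaite's method changes the degrees of freedom. Sensitivity analyses 1 and 2 add covariates, and the third adds attrition weights. The Benjamini-Hochberg check starts from the same p-values. Nesting participant within condition (item 6) adds only intercepts, which also cancel from within-participant change.

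**Working it through.** **Inputs.** From the Sample Size section: 500 per intervention arm, 1,500 in passive control, two-sided alpha 0.05, 90% power. Correlations, SDs and dropout are assumptions.

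**The plan's own figure.** Detectable d = (1.960 + 1.282) × sqrt(1/500 + 1/1,500) = 3.242 × 0.05164 = 0.167, which agrees with the stated value below 0.17. The total is 12 × 500 + 1,500 = 7,500. Neither figure is in dispute.

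**Algebra.** Write B, P and W for baseline, post-test and week 4. Under the planned model every pairwise change has variance 2σ². With complete data and a full timepoint-by-condition mean structure, the estimate of 2σ² tends to the mean M = [V(P−B) + V(W−B) + V(W−P)]/3. Hence:

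- Week-4 ratio of model SE to true SE = sqrt(M / V(W−B)). The SE is too small when 2V(W−B) exceeds V(P−B) + V(W−P), too large when it is below, and right when equal.
- Post-test ratio = sqrt(M / V(P−B)).
- Type I error = 2 × [1 − Φ(1.96 × ratio)].

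With equal SDs of 1, V = 2(1 − r). Example, correlations B-P/B-W/P-W of 0.8/0.6/0.6: the variances are 0.4, 0.8 and 0.8, so M = 0.667. Week-4 ratio = sqrt(0.667/0.8) = 0.913, type I error 7.4%. Post-test ratio = sqrt(0.667/0.4) = 1.29, type I error 1.1%.

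| r: B-P / B-W / P-W | M | Week-4 ratio | Week-4 error, complete | Week-4 error, 20% loss | Post-test ratio | Post-test error, complete |
|---|---|---|---|---|---|---|
| 0.7/0.6/0.6 | 0.733 | 0.957 | 6.1% | 6.4% | 1.11 | 3.0% |
| 0.8/0.6/0.6 | 0.667 | 0.913 | 7.4% | 8.3% | 1.29 | 1.1% |
| 0.9/0.6/0.6 | 0.600 | 0.866 | 9.0% | 10.7% | 1.73 | 0.07% |
| 0.7/0.6/0.5 | 0.800 | 1.000 | 5.0% | 5.7% | 1.15 | 2.4% |
| 0.8/0.6/0.4 | 0.800 | 1.000 | 5.0% | 6.4% | 1.41 | 0.6% |
| 0.7/0.65/0.5 | 0.767 | 1.047 | 4.0% | 4.7% | 1.13 | 2.7% |

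The 20%-loss column takes loss as completely at random at week 4. It uses the limiting random-intercept likelihood fit and compares the model SE with the sandwich SE. Expected false positives among 12 null week-4 contrasts per outcome, complete data, run from 12 × 0.040 = 0.48 to 12 × 0.090 = 1.08, against 12 × 0.05 = 0.60.

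A high same-session correlation does not by itself produce a week-4 error: the fourth and fifth sets are exact with complete data. Unequal SDs matter too. With all correlations 0.6 and a week-4 SD of 1.2, complete-data error is 5.8% at week 4 and 3.4% at post-test.

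**Simulation check.** Null data, 500 versus 1,500, 4,000 runs per cell, six sets with complete data and with 20% loss. The planned model's week-4 error ran from 3.6% to 9.4% (complete) and 4.8% to 10.8% (20% loss), following the table. Its post-test error was 0.0% to 3.8%. An unstructured fit to the same data gave 4.4% to 5.6% at both timepoints. A separate 13-arm simulation at 0.8/0.5/0.5 gave week-4 errors of 7.9%, 9.1% and 10.2% at 0%, 20% and 40% dropout under the planned model, and 4.9%, 4.8% and 4.8% under the unstructured one.

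**Cost at post-test.** Smallest effect found with 90% power = 1.96 × model SE + 1.28 × true SE. For 0.8/0.6/0.6: 1.96 × 0.0422 + 1.28 × 0.0327 = 0.125 SD, against 0.106 SD with a correct SE. For the first and third sets it is 0.138 against 0.130 and 0.108 against 0.075. At an assumed d of 0.17 the lowest power over the six sets is for 0.7/0.6/0.5: Φ[(0.17 − 1.96 × 0.0462)/0.0400] = 97.6%.

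**If the PHQ-9 has only two readings.** The primary test is at 5.0% with complete data or with equal variances. It drifts only when unequal variances and loss combine: with a week-4/baseline variance ratio of 2, to about 6.4% at 30% loss and 7.1% at 40%.

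**The case against.** - **Reach.** The problem is established only for secondary outcomes read three times, and the documents do not say how many there are. This stands, and it limits the severity.
- **Size.** Every figure rests on assumed correlations, and the largest come from one strong set, 0.9/0.6/0.6. Milder patterns give little: 0.6/0.55/0.55 gives 5.4% at week 4 with complete data and 5.6% with 20% loss. This also stands. The defect itself, one variance for all changes, needs no assumed value.
- **Post-test direction.** The six sets all make baseline to post-test the highest correlation, so post-test looks conservative by construction. Correct: 0.5/0.6/0.6 gives 6.8% at post-test and 4.1% at week 4 with complete data. This shows again that calibration depends on a pattern not yet known.
- **Unseen material.** The analysis script may use robust standard errors in the weighting analysis. Possibly, but that analysis is run only if differential attrition is found, and it would not change the main results.
- **Other remedies.** Robust standard errors on the planned model would also calibrate the tests. That is fair. However, with week-4 loss the estimates also depend slightly on the assumed covariance, and robust errors leave that unchanged. A common unstructured matrix, for its part, still assumes equal covariance across the 13 arms.

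**Conclusion.** The concern holds for the three-timepoint outcomes in secondary analyses 2, 3 and 6, and should be fixed. The planned standard errors are right at both contrasts only if all three change variances are equal. In the six assumed sets the week-4 error lies between 4.0% and 10.7%, counting complete data and 20% loss. Post-test tests are conservative there, which matters only for effects below about 0.17 SD. These ranges rest on equal SDs, assumed correlations and loss completely at random, and they are not bounds.

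For the primary PHQ-9 test the point is not established. The Primary analysis section gives timepoint three levels, but only some measures are repeated at post-test, and the Primary Hypothesis and Sample Size sections speak of baseline to follow-up. If the PHQ-9 is read at post-test, the primary tests share the problem.

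**What to change.** For three-timepoint outcomes, specify a repeated-measures model with unstructured within-participant covariance, for example R's `mmrm`, or `nlme::gls` with `corSymm` and `varIdent`. Keep the same timepoint-by-condition contrasts. If separate two-timepoint fits are preferred (baseline with post-test, baseline with week 4), allow a separate variance at each timepoint. State in the SAP which timepoints enter the PHQ-9 model.

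The cost is SAP wording, slightly more code and a move away from `lme4`/`lmerTest`. Covariance parameters rise from 2 to 6, which 7,500 participants support easily. In simulations where the planned structure is true (all correlations 0.6), the mean week-4 SE was 0.0462 against 0.0461 with no dropout, 0.0500 against 0.0499 at 20%, and 0.0558 against 0.0557 at 40%, a rise of about 0.2% or less. No new data are needed, and because collection has not begun the change can still be pre-specified.
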